Subjects will be screened for eligibility via a phone interview and an in person or telehealth evaluation. Subjects that learn about the study through StudyPages campaign ads and are recruited through the study landing page developed by StudyPages. They will complete a brief pre-screening survey to confirm interest and screen for initial inclusion criteria before being contacted by our study team for a full phone interview. The in-person or telehealth evaluation may be split into two visits if necessary.

Title : Predictors of Response to Insomnia Treatments for Gulf War Veterans
Approval Period: 08/31/2024 - 08/31/2025

At the in-person or telehealth evaluation, after signing a consent form, a more detailed interview about sleep problems, and medical and psychiatric history will be obtained by the Duke Structured Sleep Interview, including evaluations of cognitive impairment and depression. Exclusion criteria will further be evaluated by the following given solely at the office evaluation: Acute/Unstable Chronic Illness checklist, Columbia Suicide Severity Rating Scale (C-SSRS), DUKE Structured Sleep Interview, Hamilton Depression Rating Scale (HDRS24), Life Stressor Checklist, Mini International Neuropsychiatric Interview Version 5 (MINI), Montreal Cognitive Assessment (MOCA) or MOCA-Blind, Morningness-Eveningness Questionnaire, and the Sleep Related Behavior Questionnaire. Subjects will additionally be set up with PSG equipment. The PSG will be completed in the subject's own home and be used to screen a for Obstructive Sleep Apnea and Periodic Limb Movement Disorder.

Subjects will return to the lab the next morning to have the equipment removed.

Participants will be evaluated on the Anxiety and Preoccupation about Sleep Questionnaire (APSQ), Depression Anxiety and Stress Scale (DASS-21), Epworth Sleepiness Scale, and the Insomnia Severity Index each visit during weeks 1-8, and again at week 32. Sleep logs will be done daily during weeks 1-8, and again at week 32. The following will be done at weeks 1, 8, and 32: AUA8 Nocturia; Brief Pain Inventory short form (BPI-SF); Beck Anxiety Inventory (BAI); Beck Depression Inventory (BDI); Clinician Administered PTSD Scale (CAPS); Dysfunctional Beliefs and Attitudes about Sleep Scale; AUA8 (DBAS); Glasgow Content of Thoughts; Glasgow Sleep Effort Scale; Multidimensional fatigue Inventory; Penn State Worry Questionnaire (PSWQ); Perceived Stress Scale (PSS); SF-36 (RAND).

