Subjects will be evaluated on Functional Outcomes of Sleep Questionnaire at weeks 1, 2, 8 and 32.

Subjects will be evaluated on the Sleep Associated Monitoring Index (SAMI) at weeks 1 and 8.

Subjects will be evaluated on the Trial Making Test, Color Word Interference test, Thought Control Questionnaire Insomnia-Revised (TCQI), and the RBANS at weeks 1 and 32.

Following the completion of treatment at week 7, subjects will complete the Treatment Adherence Survey, Treatment Satisfaction Survey and Working Alliance Inventory. The Working Alliance Inventory will also be given at the second treatment session (week 3). If participants are participating in Telehealth, they will complete these questionnaires as RedCap surveys on Stanford's RedCap.

Blood will be drawn to measure levels of C-reactive protein (CRP). Urine samples will be collected at during each of the 3 study phases to monitor abstain from drugs of abuse, except for medical marijuana used less than four times a week. Samples will be collected by nurses at the VA Clinical Studies Unit and analyzed by the VA lab. Blood samples will be taken at the same time to be analyzed for C-reactive protein. Remaining blood will be banked to be analyzed for genetic factors.

Due to the COVID-19 pandemic, we are adding the option for participants to complete all study sessions through telehealth. We will utilize Zoom and send questionnaires as RedCap surveys on Stanford's RedCap. This will allow the participants to move forward in the study while also not deviating from the study timeline. We will still collect adverse events and study measures at each treatment session. After the COVID-19 shut-down is over, we will still offer telehealth as an option to our veterans to be flexible to their scheduling needs and keep consistency with the measures taken during

Title : Predictors of Response to Insomnia Treatments for Gulf War Veterans
Approval Period: 08/31/2024 - 08/31/2025

this crisis. Under normal circumstances, we will allow the veterans to choose if they would like to utilize telehealth or in-person treatment session and would complete all therapy sessions through the selected delivery method. We will document each individual who started therapy sessions in-person and switched to telehealth so that we can do analyses to see if their data is viable.

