(i) We plan to randomize and enroll 20-25 participants at the VA Palo Alto Health Care Systems, a Stanford-affiliated site. We plan to consent 50-60 participants total to adjust for the attrition rate of 36% (20/.36 = 55.6).

(ii) A total of 50-55 subjects are expected across all sites. There are 3 sites, at WRIISC California, located at VA Palo Alto, WRIISC New Jersey, located at VA New Jersey, and at WRIISC Washington DC, at Washington DC VA. Since the study will now have a telehealth option, the study will be open to veterans across the country.

(iii) Participants will be Gulf War Veterans with insomnia.

b) State the age range, gender, and ethnic background of the participant population being recruited.

Age Range: we expect the ages of gulf war veterans to be within the ages of 42-80.

Gender: Males and Females

Ethnic Background: Any race or ethnic origin

c) State the number and rationale for involvement of potentially vulnerable subjects in the study (including children, pregnant women, economically and educationally disadvantaged, decisionally impaired, homeless people, employees and students). Specify the measures being taken to minimize the risks and the chance of harm to the potentially vulnerable subjects and the additional safeguards that have been included in the protocol to protect their rights and welfare.

Children, pregnant women, economically and educationally disadvantaged, decisionally impaired, and homeless people will not be recruited for this protocol.

d) If women, minorities, non-English speaking individuals, or children are not included, a clear compelling rationale must be provided (e.g., disease does not occur in children, drug or device would interfere with normal growth and development, etc.).

There will be no participation of children in this study.

The research topic to be studied is irrelevant to children because we are studying military Veterans of the Gulf War.

e) State the number, if any, of participants who are laboratory personnel, employees, and/or students. They should render the same written informed consent. If payment is allowed, they should also receive it. Please see Stanford University policy.

It is unlikely that any laboratory personnel, employees, or students will qualify for participation in this study. If any do qualify and wish to participate, they will be treated the same as any other participant.

Title : Predictors of Response to Insomnia Treatments for Gulf War Veterans

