Ambulatory Overnight Sleep Recording and EEG. We will make every attempt to attach sensors carefully so that they provide the minimum discomfort possible.

Data. Paper data with PHI will be kept in locked cabinets and electronic data with PHI will be stored on physically secure and password protected computers and on the MIRECC/WRIISC server in the PAVA server room (a locked facility behind the VA firewall). Computer data backups are done by VA IT. Computers are password protected. Offices are locked when unoccupied.

Sleep Log and Questionnaires. There are no known significant risks associated with completing Sleep Logs and associated questionnaires.

Venipuncture. Experienced medical personnel will handle all the blood drawing procedures and sterile conditions will be maintained.

d) Explain the point at which the experiment will terminate. If appropriate, include the standards for the termination of the participation of the individual participant Also discuss plans for ensuring necessary medical or professional intervention in the event of adverse effects to the participants.

The experiment will end at either the normal termination or whenever the subject decides to withdraw from the study.

e) Data Safety and Monitoring Plan (DSMP). See guidance on Data Safety and Monitoring.

A Data and Safety Monitoring Plan (DSMP) is required for studies that present Medium or High risk to participants. (See Overall Evaluation of Risk above). If Low Risk, a DSMP may not be necessary. Multi-site Phase III clinical trials funded by NIH require the DSM Plan to have a Data Safety Monitoring Board or Committee (DSMC or DSMB). The FDA recommends that all multi-site clinical trials that involve interventions that have potential for greater than minimal risk to study participants also have a DSMB or DSMC.

The role of the DSMC or DSMB is to ensure the safety of participants by analyzing pooled data from all sites, and to oversee the validity and integrity of the data. Depending on the degree of risk and the complexity of the protocol, monitoring may be performed by an independent committee, a board (DSMC/DSMB), a sponsor's Data Safety Committee (DSC), a Medical Monitor, a sponsor's safety officer, or by the Protocol Director (PD).

Describe the following:

1. What type of data and/or events will be reviewed under the monitoring plan, e.g. adverse events, protocol deviations, aggregate data?

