Criteria for discontinuation of a patient in the study will include an increase in bothersome nightmares for a week under treatment. We have not seen consistent reporting of nightmares with the proposed treatments, however that is always possible, hence we would want to make sure that nightmares occurred for at least a week before a patient was discontinued. Patients will be allowed to continue in the protocol after an SAE independent of treatment, e.g. hospitalization following a fall. All treatments are considered active and patients will be allowed to continue their treatment as a courtesy. However, data from such subjects will not be included in statistical analyses since such SAEs may affect sleep. Patients will not be restarted if their sleep deteriorates meeting the above criteria and they are discontinued from the protocol.

7. Indicate to whom the data and safety monitoring person, board, or committee will disseminate the outcome of the review(s), e.g., to the IRB, the study sponsor, the investigator, or other officials, as appropriate.

Serious Adverse Events are reported to the IRB using the standard reporting forms.

8. Select One:

The Protocol Director will be the only monitoring entity for this study.

This protocol will utilize a board, committee, or safety monitor as identified in question #2 above.

10. Benefits

a) **Describe the potential benefit(s) to be gained by the participants or by the acquisition of important knowledge which may benefit future participants, etc.**

Some participants may find that their sleep is improved.

11. Privacy and Confidentiality

Privacy Protections

a) **Describe the setting and method (e.g. crowded waiting room, patient exam room, telephone or email**

Title : Predictors of Response to Insomnia Treatments for Gulf War Veterans
Approval Period: 08/31/2024 - 08/31/2025

communication) in which interactions will occur and how the privacy interests of participants will be maintained. Note, high risk data such as PHI must be sent via "Secure:" email per Stanford policy.

During screening, participants will meet in a private interview room with a member of the study team to sign the consent form, discuss the protocol, and determine suitability for enrollment. All interviews will be done in a private setting. Samples will be obtained in a private setting.

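### Adherence and satisfaction are surveyed only on completion of treatment at week 7, with nothing planned at early stopping, so the results will mainly describe completers

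*Protocol*

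**What the plan says.** Section 2 (Study Procedures), a) sets the timing: "Following the completion of treatment at week 7, subjects will complete the Treatment Adherence Survey, Treatment Satisfaction Survey and Working Alliance Inventory". Adherence and satisfaction have no other time point in the protocol. Alliance has one more: "The Working Alliance Inventory will also be given at the second treatment session (week 3").

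The neighbouring measures in the same section are tied to visits or numbered weeks, for example "Sleep logs will be done daily during weeks 1-8, and again at week 32". The adherence and satisfaction surveys are tied to finishing treatment.

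Two passages in section 9 (Risks) bear on people who do not finish. Item d) says: "The experiment will end at either the normal termination or whenever the subject decides to withdraw from the study". Item e), question 6, provides for stopping during treatment: "Criteria for discontinuation of a patient in the study will include an increase in bothersome nightmares for a week under treatment". Neither passage describes a closing assessment for these participants, and none appears elsewhere in the protocol.

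**The concern.** Low adherence and dissatisfaction are plausible reasons for leaving a talking or behavioural treatment early. If the forms that measure them are handed out only when treatment is complete, whether a person has a score depends partly on what the score would have been. The missing values are then selective, and no later analysis can recover answers that were never asked for. This is why the point belongs in the protocol rather than in an analysis plan.

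The study asks who benefits from sleep restriction (SR) and who from cognitive therapy (CT), and it also plans mediator measures. For that purpose a participant who carried out the treatment without benefit differs from one who did not carry it out. Adherence known mainly in completers blurs the distinction among those who left early. At stake is the reading of process measures. The main hypothesis, about baseline predictors, does not depend on them.

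**Working it through.** The protocol states no figure on this point, so there is none to reproduce. The check has three steps.

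**1. Is there a usable stopping rate?** The only attrition figure is in section 8 a): "We plan to consent 50-60 participants total to adjust for the attrition rate of 36% (20/.36 = 55.6"). The division is right: 20 / 0.36 = 55.6. But allowing for a 36% loss would give 20 / (1 − 0.36) = 31.25, so 32. As used, 36% is the share of consented people who go on to be randomised. It is not a rate of stopping treatment, and a rate has to be assumed.

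**2. What would completer-only data do to a mean?** Let d be the share of randomised participants who stop early, A_c the completers' mean and A_s the mean the stoppers would have given. Then

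completers' mean − mean of all randomised = A_c − [(1 − d) × A_c + d × A_s] = d × (A_c − A_s).

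All inputs here are assumptions: a 0–100 scale, A_c = 80, and d from 10% to 36% (the upper end is only a convenient bound). Overstatement in points:

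| Stoppers' mean | d = 10% | d = 20% | d = 30% | d = 36% |
|---|---|---|---|---|
| 80 | 0 | 0 | 0 | 0 |
| 60 | 2.0 | 4.0 | 6.0 | 7.2 |
| 40 | 4.0 | 8.0 | 12.0 | 14.4 |
| 20 | 6.0 | 12.0 | 18.0 | 21.6 |

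For head counts, section 8 a) gives the current target: "A total of 50-55 subjects are expected across all sites". At these rates, between 50 × 0.10 = 5 and 55 × 0.36 = 19.8 (about 20) participants would lack the surveys.

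For a difference between arms measured on the same form, the shift is d_1 × gap − d_2 × gap. With a 40-point gap in both arms, 30% against 10% stopping gives 12 − 4 = 8 points; equal stopping gives 0. This applies only to a measure that shares one scale across arms. The attachments in section 16 list separate adherence questionnaires for BT and CT, so it should not be read as a bias in an adherence comparison.

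**3. What else is recorded for someone who stops early?**

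- Alliance: one rating, if the participant reached week 3.
- SR adherence: the daily sleep logs record time in bed until participation ends.
- Attendance: sessions are paid individually (section 8 k), so a count should exist.
- CT adherence: the logs do not show whether the cognitive techniques were practised, and no other scheduled form does.
- Satisfaction: nothing in either arm.

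The partial cover is therefore better for SR than for CT.

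**The case against.** The strongest reply is that the trigger can be read as a date. The second session is in week 3, so six weekly sessions end in week 7, and the sentence may simply mean the end of the fixed treatment phase. Section 9 d) concerns someone who leaves the study. Someone who only stops attending therapy is not barred from answering at week 7. This stands. A reader might infer that early stoppers can never supply these data, but that comes from silence and the text does not say it. For people who withdraw or are discontinued, however, the date reading does not help.

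A reader might also infer that non-response cannot be told apart from not doing the treatment. That goes too far. Sleep logs, symptom scales at each visit, session recordings and attendance all give some information up to the point of stopping. What remains uncovered is CT adherence and satisfaction.

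Third, no adherence or acceptability endpoint is named, no comparison of arms on these surveys is stated, and the primary hypothesis concerns baseline characteristics. This stands and limits the weight of the point.

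Fourth, section 2 a) is a summary by design, and attachments that are not shown could describe an early-stopping procedure. That is possible, but the protocol text does not point to one.

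Finally, the change may come too late. Section 8 m) says analysis is taking longer than expected, and section 16 lists a 2023 monitoring-board closing report and closure documents for the other sites. This affects which remedy applies, but the limitation on the data remains.

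**Conclusion.** The point holds as a cheap improvement of minor to moderate weight. As written, adherence, satisfaction and end-of-treatment alliance will come mainly from participants who finished treatment, and the adherence and satisfaction summaries are likely to be too favourable.

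The direction rests on two assumptions: that some participants stop early, and that stoppers would score lower. The protocol establishes neither, so the tempting conclusion that both arms are overstated is not supported as a fact. The size cannot be derived from the protocol. The range of 2.0 to 21.6 points in the table is illustrative, and the bias is zero if stoppers score like completers. A distorted adherence comparison between arms is not shown either, because the adherence forms differ by arm and no such comparison is stated.

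**What to change.** Change the trigger in section 2 a). Give the Treatment Adherence Survey, the Treatment Satisfaction Survey and the Working Alliance Inventory to every randomised participant at week 7, or at the time of stopping therapy if that is earlier. Offer them as part of the stopping contact, since section 9 d) ends participation on withdrawal. Use the REDCap surveys already set up for telehealth participants where possible. Report sessions attended for all randomised participants, so that something is known about those who do not answer.

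The cost is one sentence in the schedule and one extra contact per early stopper, which some will decline. The bias term d × (A_c − A_s) falls to zero only if all stoppers respond; partial response reduces the missing data without guaranteeing that the bias goes.

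If data collection is already over, label the adherence, satisfaction and end-of-treatment alliance results as completer-only, give the number missing in each arm, and report sessions attended for everyone randomised. This needs no new data, provided attendance was kept.

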After screening and randomization in the 2-week baseline phase, subjects will receive SR or CT in the 6-week treatment phase. Participants will have the option to complete study sessions over telehealth for the entirety of the 6 weeks. There will be no more treatment after this point. At the end of the 6-week treatment, subjects will return to repeat many of the psychological tests administered during baseline to determine the short-term benefit. This 4-year proposal will include 100 subjects (2 groups of 50 each) with outcome, mediator and moderator measures collected at appropriate points.

All subjects will receive education about basic sleep hygiene as well as information about the science of sleep including sleep stages and sleep regulation.

Sleep Restriction Therapy (SR). The initial Time in Bed (TIB) prescription is calculated on the average total sleep time (TST) reported in the baseline sleep logs.

After one week, depending on subject's daily sleep logs, the therapist suggests a new TIB prescription. Napping is neither prescribed nor proscribed. However, if subjects find themselves very sleepy (not just tired, but actually sleepy) they are advised to take a brief (15 to 30 minutes) nap to ensure their safety.

Cognitive Therapy (CT). The CT treatment module is designed to meet three general goals:

1) identification of dysfunctional sleep cognitions, 2) challenging their validity, and 3) replacing them with more adaptive substitutes.

Several specific techniques designed to meet these goals are discussed

in materials distributed to subjects. Similar to SR, subjects in CT are given information about relevant elements of the science of sleep and healthy sleep practices.

We will also continue to monitor progress post-treatment in the follow-up period. The complete package of outcome measures will be repeated at the follow-up session. We will tell subjects that we expect the benefits of treatment to continue and/or improve with time and we will also encourage subjects to continue practicing the treatment instructions to maintain their progress after active treatment ends.

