Subjects will be screened for eligibility via a phone interview and an in person or telehealth evaluation. The in-person or telehealth evaluation may be split into two visits if necessary. At the in-person or telehealth evaluation, after signing a consent form, a more detailed interview about sleep problems, and medical and psychiatric history will be obtained by the Duke Structured Sleep Interview, including evaluations of cognitive impairment and depression. Exclusion criteria will further be evaluated by the following given solely at the office evaluation: Berlin Questionnaire, Life Stressor Checklist, Columbia Suicide Severity Rating Scale (C-SSRS), Acute/Unstable Chronic Illness checklist, Mini International Neuropsychiatric Interview Version 5 (MINI), Morningness-Eveningness Questionnaire, Montreal Cognitive Assessment (MOCA) or MOCA-Blind, Thought Control Questionnaire Insomnia-Revised (TCQI), and the Mini-Mental State Exam (MMSE). If the session is conducted in-person, subjects will additionally be set up with PSG equipment. The PSG will be completed in the subject's own home and be used to screen for Obstructive Sleep Apnea and Periodic Limb Movement Disorder. Subjects will return to the lab the next morning to have the equipment removed.

At that time a brief physical exam will be conducted including cardiopulmonary and neurological status. Potential subjects will complete 1 week of daily sleep logs, which will serve as a further screening to insure that subjects' insomnia severity meets our entry criteria. Baseline sleep logs will also serve to screen for certain disorders such as a non-24-h sleep-wake syndrome or an irregular sleep-wake pattern (i.e., ≥ 3 sleep episodes during a 24-h period indicating an absence of a circadian rhythm). Potential participants will also undergo relevant psychological tests, and medical, psychiatric, and medication histories will be gathered and evaluated. Subjects taking sleeping medications at the time of recruitment will be admitted to the study if under the supervision of their physician they remain stable on the medication for a minimum of 3 weeks before acceptance into the protocol.

Participants who complete a screening session via telehealth will not undergo a physical but will complete all other screening measures.

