Participants from other sites can be referred to Palo Alto for screening. They will be given our phone number and told to contact us. We will follow the remote screening procedures outlines above for these participants.

j) Describe how you will be cognizant of other protocols in which participants might be enrolled. Please explain if participants will be enrolled in more than one study.

We will ask the potential subject if they are participating in any other protocols, and document this on the consent form. They will be instructed not to participate in any other protocols during their involvement with our study without first getting prior authorization from both our research team and that of the other study. Overlapping participation will be handled on a case-by-case basis.

k) Payment/reimbursement. Explain the amount and schedule of payment or reimbursement, if any, that will be paid for participation in the study. Substantiate that proposed payments are reasonable and commensurate with the expected contributions of participants and that they do not constitute undue pressure on participants to volunteer for the research study. Include provisions for prorating payment. See payment considerations

Participants will receive \$150 for the screening procedures including the PSG. If the participant is determined to be eligible for the study, s/he will receive stipends of \$25 for each of the 6 treatment visits thereafter and \$25 for the follow up visit $7 \times \$25 = \175 . Participants who complete all treatment visits and the follow up, which includes a second PSG overnight, visit will receive a \$150 completion bonus. Thus, participants who complete all the study visits will receive a total of \$475.

If a participant completes the study through telehealth, they will receive \$50 for the screening procedures. If the participant is determined to be eligible for the study, s/he will receive stipends of \$25 for all 6

Title : Predictors of Response to Insomnia Treatments for Gulf War Veterans
Approval Period: 08/31/2024 - 08/31/2025

treatment visits thereafter and \$25 for the follow up visit ($7 \times \$25 = \175). Participants who complete all treatment visits and the follow up visit will receive a \$50 completion bonus. These stipends are intended to encourage compliance with the research protocol without adding undue influence.

I) Costs. Please explain any costs that will be charged to the participant.

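### Does the one-week mismatch in week numbering let nights under sleep restriction into the baseline sleep-log measure?

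*Protocol*

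**What the plan says.** Section 2(a) sets out the phases: "After screening and randomization in the 2-week baseline phase, subjects will receive SR or CT in the 6-week treatment phase". Logs cover the whole span: "Sleep logs will be done daily during weeks 1-8, and again at week 32". Further on, the same section fixes two points by week number: "The Working Alliance Inventory will also be given at the second treatment session (week 3"), and "Following the completion of treatment at week 7, subjects will complete the Treatment Adherence Survey" along with two other questionnaires. The payment text in Section 8(k) gives the number of sessions, a stipend being paid "for each of the 6 treatment visits thereafter".

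Two statements concern the baseline log itself. On screening, Section 8(i) says: "Potential subjects will complete 1 week of daily sleep logs". On the SR arm, Section 2(a) says: "The initial Time in Bed (TIB) prescription is calculated on the average total sleep time (TST) reported in the baseline sleep logs".

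Section 1(b) names excess time in bed at baseline as the expected predictor of response to SR. It gives neither an instrument nor a time window for it.

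**The concern.** On a plain reading the two sets of week numbers do not fit. A 2-week baseline occupies weeks 1 and 2, yet a second session in week 3 puts the first in week 2. At the other end, week 8 is the last treatment week by the phase lengths but comes after the end of treatment by the session weeks. The single week of screening logs in Section 8(i) adds doubt about how long the baseline log is.

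Time in bed is what SR reduces from its first session. A baseline mean of time in bed that took in nights after that session would be lowered in the SR arm only and would no longer be a baseline variable. Adjusting for it could create a false difference between arms, and testing its interaction with arm could distort the moderator analysis that carries the primary hypothesis.

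**Working it through.** **Inputs.** Baseline 2 weeks and treatment 6 weeks; second session at week 3; treatment complete at week 7; daily logs in weeks 1 to 8; batteries at weeks 1, 8 and 32 (all Section 2(a)). Six treatment visits (Section 8(k)). One week of screening logs (Section 8(i)). Weekly spacing of the six visits is inferred.

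**Reading 1: week numbers are intervals, counted from the phase lengths.**
- First treatment week: 2 + 1 = 3. Last: 2 + 6 = 8.
- Second session: 2 + 2 = week 4. Stated: week 3. Difference: 1 week.
- Last session: week 8. Stated: week 7. Difference: 1 week.

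The stated weeks are not reproduced on this reading.

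**Reading 2: count from the stated session weeks.**
- Session 2 at week 3 means that session k falls at week k + 1.
- Session 1 falls at week 2 and session 6 at week 7.

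The sixth session lands on the stated completion week, so the session weeks and the number of visits agree with each other.

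**Reading 3: week number w means the end of w weeks (a visit time point).**
- Session 1 at week 2 leaves 2 full weeks before it, which is the stated baseline.
- Session 6 is at week 7, and the week 8 battery follows one week later.
- From session 1 to the battery: 8 − 2 = 6 weeks, which is the stated treatment phase.

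All the stated figures agree on this reading. The protocol does not state this convention, but nothing in it rules the convention out.

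**Baseline log length.** Section 2(a) places screening inside the 2-week baseline phase. One week of screening logs can sit within two weeks, so the statements need not conflict. It remains unclear whether the baseline log is one week or two.

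**Order of log and treatment.** The first SR prescription is computed from the baseline logs. A log that is an input to a prescription was recorded before it. Section 2(a) also has treatment follow the baseline phase. Randomisation inside that phase does no harm, since treatment comes after it.

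**Exposure if this order were ignored.** Suppose an analyst averaged weeks 1 and 2 whatever the session date, and session 1 fell on day d of week 2. Nights after the session are 8 − d out of 14:
- d = 1: 7 of 14.
- d = 7: 1 of 14.
- Window closed at session 1: 0.

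**Size in that case.** The inputs below are assumptions, not protocol figures, apart from N, which lies within the 50–55 of Section 8(a): N = 52; excess time in bed with mean 2.5 h and SD 0.8 h; week-to-week SD 0.4 h; SR removes 50% to 100% of the excess; outcome correlated 0.3 to 0.5 with the excess; no true arm effect and no moderation. With all of week 2 under SR, the two-week mean falls by 0.5 × (50% to 100%) × 2.5 h = 0.625 to 1.25 h. Simulated rejection at a nominal 5%:

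| Week 2 nights after session 1 | Arm effect adjusted for this mean | Interaction with arm |
|---|---|---|
| All | 12–61% | 5–11% (up to 17% in one set of runs) |
| Half | 7–30% | 5–8% |
| One of seven | 5–7% | 4–6% |
| None (log days before session 1 only) | about 5% | about 5% |

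The large figures belong to an adjusted main-effect comparison, which the protocol does not specify. The stated primary hypothesis is moderation, the right-hand column.

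**The case for a change.** The best case for a change is that the protocol itself prints the week numbers, so this is not detail left to a SAP. No convention is written down, several sites need one rule, and the variable at risk is the one that SR alters. Dated daily logs already exist, so a rule tied to session dates would cost only wording. It could be argued as well that the prescription sentence sharpens the conflict: baseline logs must be complete before session 1, yet session 1 falls in what reads as the second baseline week.

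Part of this stands. The numbering is unclear on a plain reading, the length of the baseline log is not settled, and on the interval reading the place of week 8 relative to the end of treatment is unclear too. The harm does not follow. The only averaging the protocol describes is of total sleep time, to set the first prescription; it nowhere says that time in bed is averaged over two calendar weeks for analysis. If session 1 does fall early in week 2, the logs that set the prescription are simply the nights before it. The sleep log is the natural source for excess time in bed, but Section 1(b) does not name it, and the window for a derived variable is commonly left to a SAP, which is not at hand.

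**Conclusion.** No change to the plan is called for. The one-week difference is real if week numbers are intervals and disappears if they are visit time points. On either reading the logs behind the first SR prescription precede treatment, so the plan followed as written brings no treated nights into baseline. Taking baseline from log days before the first session, and post-treatment from days after the last, is what analysts would do from the dated daily logs; writing it down would record what the plan already implies.

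The bias figures hold only if the two-week window is averaged past session 1, much of week 2 lies under SR, and the assumed inputs apply. For the moderation test, the simulated rejection rate then mostly stays between 5% and 11%, and it is about 5% when the window closes at session 1. What is left is clerical: the week numbers and the baseline log length are unclear between Sections 2(a) and 8(i), and those passages should be reconciled when the text is next tidied. This note takes no position on which treatment schedule is right.
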